|   |                |   | 
 
– The prompt diagnosis of immune-mediated peripheral neuromotor syndromes is important, since certain patients may unpredictably experience acute decompensations that can result in substantial morbidity or in the worst case, death. Special care should be taken for certain sentinel symptoms that may predict a more severe outcome, such as prominent dysphagia, rapidly progressive weakness, and signs of respiratory insufficiency or autonomic instability.
 
– Patients should be evaluated to rule out any alternative etiology (e.g., disease progression, infections, metabolic syndromes or medications). It should be noted that the diagnosis of immune-mediated peripheral neuromotor syndromes can be particularly challenging in patients with underlying cancer, due to the multiple potential confounding effects of cancer (and its treatments) throughout the neuraxis. Given the importance of prompt and accurate diagnosis, it is essential to have a low threshold to obtain a neurological consult.
 
– Neurophysiologic diagnostic testing (e.g., electromyogram and nerve conduction investigations, and “repetitive stimulation” if myasthenia is suspected) are routinely indicated upon suspicion of such conditions and may be best facilitated by means of a neurology consultation.
 
– It is important to consider that the use of steroids as the primary treatment of Guillain-Barre is not typically considered effective. Patients requiring treatment should be started with IV IG and followed by plasmapheresis if not responsive to IV IG.
 
 |
|   | Grade 1 | No dose modifications.  | For Grade 1: 
 
– Consider, as necessary, discussing with the study physician.
 
– Care should be taken to monitor patients for sentinel symptoms of a potential decompensation as described above.
 
– Obtain a neurology consult.
 
  |
|   | Grade 2 | Hold study drug/study regimen dose until resolution to Grade $\leq 1$ . | For Grade 2: 
 
– Consider, as necessary, discussing with the study physician.
 
– Care should be taken to monitor patients for sentinel symptoms of a potential decompensation as described above.
 
– Obtain a neurology consult
 
   |

---

|  |  |
|--|--|
| 
or if there are signs of respiratory insufficiency or autonomic instability.
  | 
 
– Sensory neuropathy/neuropathic pain may be managed by appropriate medications (e.g., gabapentin or duloxetine).
 
 
MYASTHENIA GRAVIS:
 
 
○ Steroids may be successfully used to treat myasthenia gravis. It is important to consider that steroid therapy (especially with high doses) may result in transient worsening of myasthenia and should typically be administered in a monitored setting under supervision of a consulting neurologist.
 
○ Patients unable to tolerate steroids may be candidates for treatment with plasmapheresis or IV IG. Such decisions are best made in consultation with a neurologist, taking into account the unique needs of each patient.
 
○ If myasthenia gravis-like neurotoxicity is present, consider starting AChE inhibitor therapy in addition to steroids. Such therapy, if successful, can also serve to reinforce the diagnosis.
 
 
GUILLAIN-BARRE:
 
 
○ It is important to consider here that the use of steroids as the primary treatment of Guillain-Barre is not typically considered effective.
 
○ Patients requiring treatment should be started with IV IG and followed by plasmapheresis if not responsive to IV IG.
 
 
For Grade 3 or 4 (severe or life-threatening events):
 
 
– Consider, as necessary, discussing with study physician.
 
– Recommend hospitalization.
 
– Monitor symptoms and obtain neurological consult.
 
 
MYASTHENIA GRAVIS:
 
 
○ Steroids may be successfully used to treat myasthenia gravis. They should typically be administered in a monitored setting under supervision of a consulting neurologist.
 
○ Patients unable to tolerate steroids may be candidates for treatment with plasmapheresis or IV IG.
 
 |
| 
Grade 3 or 4
 
For Grade 3:
 
Hold study drug/study regimen dose until resolution to Grade <math>\leq 1</math>.
 
Permanently discontinue study drug/study regimen if Grade 3 imAE does not resolve to Grade <math>\leq 1</math> within 30 days or if there are signs of respiratory insufficiency or autonomic instability.
 |  |

---

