## 6.4 Protocol Therapy Discontinuation

In addition to discontinuation from therapy related to toxicities as outlined in Appendix 1, a subject will also be discontinued from protocol therapy and followed per protocol under the following circumstances outlined below. The reason for discontinuation of protocol therapy will be documented on the electronic case report form (eCRF)

- Confirmed disease progression per RECIST 1.1 prior to Cycle 7
- Completion of scheduled treatment
- Site investigator determines a change of therapy would be in the best interest of the subject
- Subject requests to discontinue protocol therapy, whether due to unacceptable toxicity or for other reasons
  - In a subject decides to prematurely discontinue protocol therapy (“refuses treatment”), the subject should be asked if he or she may still be contacted for further scheduled study assessments. The outcome of that discussion should be documented in both the medical records and in the eCRF.
- Female subject becomes pregnant.
- If subject weight falls to 35kg or less.

- Grade  $\geq 3$  infusion reaction.
- Study therapy is interrupted for  $\geq 120$  days.

Subjects who are permanently discontinued from receiving investigational product will be followed for safety per Section 7, including the collection of any protocol-specified blood specimens, unless consent is withdrawn or the subject is lost to follow-up or enrolled in another clinical study. All subjects will be followed for survival. Subjects who decline to return to the site for evaluations will be offered follow-up by phone every 3 months as an alternative.

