| 
Drug administration modifications of study drug/study regimen will be made to manage potential immune-related AEs based on severity of treatment-emergent toxicities graded per NCI CTCAE v4.03.
 
In addition to the criteria for permanent discontinuation of study drug/study regimen based on CTC grade/severity (table below), permanently discontinue study drug/study regimen for the following conditions:
 
 
• Inability to reduce corticosteroid to a dose of <math>\leq 10</math> mg of prednisone per day (or equivalent) within 12 weeks after last dose of study drug/study regimen
 
• Recurrence of a previously experienced Grade 3 treatment-related AE following resumption of dosing
 
 
Grade 1      No dose modification
 
Grade 2      Hold study drug/study regimen dose until Grade 2 resolution to Grade <math>\leq 1</math>.
 
If toxicity worsens, then treat as Grade 3 or Grade 4.
 
Study drug/study regimen can be resumed once event stabilizes to Grade <math>\leq 1</math> after completion of steroid taper.
 
Patients with endocrinopathies who may require prolonged or continued steroid replacement can be retreated with study drug/study regimen on the following conditions:
 
 
1. The event stabilizes and is controlled.
 
2. The patient is clinically stable as per Investigator or treating physician's clinical judgement.
 
3. Doses of prednisone are at <math>\leq 10</math> mg/day or equivalent.
 
 | 
It is recommended that management of immune-mediated adverse events (imAEs) follows the guidelines presented in this table:
 
 
– It is possible that events with an inflammatory or immune mediated mechanism could occur in nearly all organs, some of them not noted specifically in these guidelines.
 
– Whether specific immune-mediated events (and/or laboratory indicators of such events) are noted in these guidelines or not, patients should be thoroughly evaluated to rule out any alternative etiology (e.g., disease progression, concomitant medications, and infections) to a possible immune-mediated event. In the absence of a clear alternative etiology, all such events should be managed as if they were immune related. General recommendations follow.
 
– Symptomatic and topical therapy should be considered for low-grade (Grade 1 or 2, unless otherwise specified) events.
 
– For persistent (<math>>3</math> to 5 days) low-grade (Grade 2) or severe (Grade <math>\geq 3</math>) events, promptly start prednisone 1 to 2 mg/kg/day PO or IV equivalent.
 
– Some events with high likelihood for morbidity and/or mortality – e.g., myo-carditis, or other similar events even if they are not currently noted in the guidelines – should progress rapidly to high dose IV corticosteroids (methylprednisolone at 2 to 4 mg/kg/day) even if the event is Grade 2, and if clinical suspicion is high and/or there has been clinical confirmation. Consider, as necessary, discussing with the study physician, and promptly pursue specialist consultation.
 
– If symptoms recur or worsen during corticosteroid tapering (28 days of taper), increase the corticosteroid dose (prednisone dose [e.g., up to 2 to 4 mg/kg/day PO or IV equivalent]) until stabilization or improvement of symptoms, then resume corticosteroid tapering at a slower rate (<math>>28</math> days of taper).
 
– More potent immunosuppressives such as TNF inhibitors (e.g., infliximab) (also refer to the individual sections of the imAEs for specific type of immunosuppressive) should be considered for events not responding to systemic steroids. Progression to use of more potent immunosuppressives should proceed more rapidly in events with high likelihood for morbidity and/or mortality – e.g., myocarditis, or other similar events even if they are not currently noted in the guidelines – when these events are not responding to systemic steroids.
 
– With long-term steroid and other immunosuppressive use, consider need for Pneumocystis jirovecii pneumonia (PJP, formerly known as Pneumocystis carinii pneumonia) prophylaxis, gastrointestinal protection, and glucose monitoring.
 
 |

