**For Grade 4:**

Permanently discontinue study drug/study regimen.

| Nephritis or renal dysfunction | Any Grade              | General Guidance    | For Any Grade:   |
|--------------------------------|------------------------|---------------------|--|
| (elevated serum creatinine)    |                        |                     | 
 
– Consult with nephrologist.
 
– Monitor for signs and symptoms that may be related to changes in renal function (e.g., routine urinalysis, elevated serum BUN and creatinine, decreased creatinine clearance, electrolyte imbalance, decrease in urine output, or proteinuria).
 
– Patients should be thoroughly evaluated to rule out any alternative etiology (e.g., disease progression or infections).
 
– Steroids should be considered in the absence of clear alternative etiology even for low-grade events (Grade 2), in order to prevent potential progression to higher grade event.
 
 |
| Grade 1                 | No dose modifications. | For Grade 1: | 
 
– Monitor serum creatinine weekly and any accompanying symptoms. 
 
• If creatinine returns to baseline, resume its regular monitoring per study protocol.
 
• If creatinine worsens, depending on the severity, treat as Grade 2, 3, or 4.
 
 
 
– Consider symptomatic treatment, including hydration, electrolyte replacement, and diuretics.
 
   |

|   |  |   |
|---|--|---|

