| Grade 2
(serum creatinine $>1.5$ to $3.0 \times$ baseline; $>1.5$ to $3.0 \times$ ULN)  | Hold study drug/study regimen until resolution to Grade $\leq 1$ or baseline. 
 
• If toxicity worsens, then treat as Grade 3 or 4.
 
• If toxicity improves to Grade <math>\leq 1</math> or baseline, then resume study drug/study regimen after completion of steroid taper.
 
 | For Grade 2: 
 
– Consider symptomatic treatment, including hydration, electrolyte replacement, and diuretics.
 
– Carefully monitor serum creatinine every 2 to 3 days and as clinically warranted.
 
– Consult nephrologist and consider renal biopsy if clinically indicated.
 
– If event is persistent (<math>>3</math> to 5 days) or worsens, promptly start prednisone 1 to 2 mg/kg/day PO or IV equivalent.
 
– If event is not responsive within 3 to 5 days or worsens despite prednisone at 1 to 2 mg/kg/day PO or IV equivalent, additional workup should be considered and prompt treatment with IV methylprednisolone at 2 to 4 mg/kg/day started.
 
– Once the patient is improving, gradually taper steroids over <math>\geq 28</math> days and consider prophylactic antibiotics, antifungals, and anti-PJP treatment (refer to current NCCN guidelines for treatment of cancer-related infections [Category 2B recommendation]).a
 
– When event returns to baseline, resume study drug/study regimen and routine serum creatinine monitoring per study protocol.
 
 |

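### Appendix 1, Grade 2 nephritis: one bullet says to resume tremelimumab at baseline creatinine and omits the completed steroid taper that the dose column of the same row requires

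*Combined protocol and SAP*

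**What the plan says.** The row in question is Nephritis or renal dysfunction, Grade 2, under Specific Immune-Mediated Reactions in Appendix 1.

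- **Dose column.** Drug is held until the event is Grade 1 or lower or back at baseline. If that happens, the instruction is "then resume study drug/study regimen after completion of steroid taper".
- **Management column.** Prednisone at 1 to 2 mg/kg/day is started if the event persists beyond 3 to 5 days or worsens. Once the patient improves, steroids are tapered over at least 28 days. The last bullet then reads: "When event returns to baseline, resume study drug/study regimen and routine serum creatinine monitoring per study protocol".

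The General Considerations table at the head of Appendix 1 has its own Grade 2 rule. It begins "Study drug/study regimen can be resumed once event stabilizes to Grade" 1 or lower, and it too adds completion of the taper.

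The two columns differ in force. The dose column opens with "Drug administration modifications of study drug/study regimen will be made to manage potential immune-related AEs", the management column with "It is recommended that management of immune-mediated adverse events (imAEs) follows the guidelines presented in this table". Section 11.1.3 describes the guidelines as prepared by the funder to assist clinical judgment. Section 6.2 refers sites to them and tells the investigator to consult the sponsor-investigator when in doubt. Nothing in the protocol states which column prevails if they disagree.

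**The concern.** The bullet is a direct instruction to give drug, with a return to baseline as its only stated condition. A site working down the management column could reach it with the patient still on a steroid dose that the dose column treats as a reason to wait.

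Elsewhere, Appendix 1 is careful about dosing on steroids. Its exception, "Patients with endocrinopathies who may require prolonged or continued steroid replacement can be retreated with study drug/study regimen on the following conditions", is tied to three conditions, one of them prednisone at no more than 10 mg/day. The nephritis bullet carries no such limit. At stake is the timing of a dose in a patient recovering from immune-mediated kidney injury, and whether sites handle such patients in the same way.

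**Working it through.** The plan gives no figure to reproduce. The check compares the texts and then bounds the consequence.

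**1. The conditions side by side**

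| Place in Appendix 1 | Condition on the event | Condition on the taper |
|---|---|---|
| Grade 2 nephritis, dose column | Grade 1 or lower, or baseline | completed |
| General Considerations, Grade 2 | Grade 1 or lower | completed |
| Grade 2 nephritis, last management bullet | baseline | none stated |

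The Grade 2 dose cells for pneumonitis, colitis, hepatitis, rash, endocrinopathy, neurotoxicity and myocarditis also require a completed taper. No other Grade 2 management cell that can be read in the available text tells the site to resume drug (part of the myositis cell is lost). The bullet therefore looks like a drafting slip.

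**2. When the two rules part**

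They part only if steroids were given, since otherwise there is no taper. The taper begins at improvement, which can precede or coincide with the return to baseline. Baseline during the taper is therefore possible.

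**3. How much earlier the bullet could allow a dose**

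Count days from the start of the taper. Let T be its length (at least 28), b the day baseline is reached (b no later than T, no relapse), and D the day the next dose falls due (negative if overdue).

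- Bullet alone: earliest dose on day max(b, D).
- Dose column: earliest dose on day max(T, D).
- Difference: max(0, T − max(b, D)).

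With T = 28:

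| Situation | Days earlier |
|---|---|
| Dose already due, b = 0 | 28 − 0 = 28 |
| Dose already due, b = 7 | 28 − 7 = 21 |
| Dose already due, b = 14 | 28 − 14 = 14 |
| Dose already due, b = 21 | 28 − 21 = 7 |
| b = 7, dose due on day 21 | 28 − 21 = 7 |
| Dose due on day 28 or later | 0 |

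The 28-day case needs baseline on the day the taper starts, when the patient need only be improving, and a dose already due. A longer taper widens the window. Under Section 6.4, therapy stops only after an interruption of 120 days or more. Waiting out a minimum taper uses at most 28/120 = 23% of that.

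**4. Steroid dose at that point (assumption: linear taper to zero over 28 days)**

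Dose on day d is S × (1 − d/28), where S is the starting dose. It reaches 10 mg/day on day 28 × (1 − 10/S). The 35 kg case is the lower limit, because Section 6.4 stops therapy "If subject weight falls to 35kg or less"; 70 kg is an assumed weight.

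| Starting dose S | Day 7 | Day 14 | Day 21 | Reaches 10 mg/day |
|---|---|---|---|---|
| 35 mg (35 kg, 1 mg/kg) | 26.25 mg | 17.5 mg | 8.75 mg | day 20 |
| 70 mg (70 kg, 1 mg/kg) | 52.5 mg | 35 mg | 17.5 mg | day 24 |
| 140 mg (70 kg, 2 mg/kg) | 105 mg | 70 mg | 35 mg | day 26 |

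**5. How many patients**

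The documents give no rate, so both inputs are assumed: Grade 2 nephritis in 2% to 10%, and 25% to 75% of those both given steroids and at baseline before the taper ends. The range is 28 × 0.02 × 0.25 = 0.14 to 28 × 0.10 × 0.75 = 2.1 of 28 subjects. These are patients who would meet the conflicting wording; fewer would be dosed early.

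**The case against.** The strongest reply is that the row, read whole, is clear. The column that governs dosing states the taper condition, the general Grade 2 rule repeats it, and the dose column is worded more firmly than the management column. The bullet comes straight after the taper bullet and can be read in sequence; it omits the taper rather than waiving it. For a patient who never had steroids it needs no qualifier.

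There are other safeguards. Section 5.2.2 restricts systemic steroids above 10 mg/day. Appendix 1 stops drug for good if steroids cannot be brought down to 10 mg/day within 12 weeks of the last dose. Creatinine must be reviewed within 3 days before each dose, and a nephrologist is consulted at any grade.

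Most of this stands, and it is why the risk is small. It does not remove the contradiction. The bullet's trigger is the return to baseline, not the end of the taper. The Section 5.2.2 restriction exempts short-term steroids for emergent events related to study drug. Advice to consult when in doubt helps only a site that notices the conflict.

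Two stronger readings are tempting and not supported:

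- A reader might infer a conflict in the other direction, with a patient at Grade 1 after the taper allowed to resume by the dose column and barred by the bullet. The bullet does not say that drug may be resumed only at baseline, so it bars nothing.
- A reader might set the lowest starting dose, 35 mg/day, against the 10 mg/day cap and conclude that patients would be re-dosed at 3.5 times the cap or more. That is the dose at the start of the course. The dose at re-dosing depends on the day of the taper and, in the lightest patient above, is under 10 mg/day by day 21.

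**Conclusion.** The row is wrong as written: it contains an internally contradictory dosing rule. The severity is minor. For patients given steroids, the last management bullet read alone permits a dose during the taper that the dose column forbids. The early dosing cannot exceed the part of the taper that remains after the next dose is due, so it is between 0 and 28 days for a minimum-length taper.

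The day counts assume a 28-day taper and no relapse. The steroid levels assume a linear taper, and the patient numbers rest on assumed rates. The contradiction itself rests on none of these.

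A reader might infer that the trial's error rates or safety monitoring are compromised. They are not. The Simon rule counts responses, and the stopping rule in Section 12.7 counts treatment-related events of Grade 3 or higher. Neither boundary depends on when drug is resumed after a Grade 2 event.

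**What to change.** Split the two actions in the last management bullet of the Grade 2 nephritis row. Suggested wording: *Resume study drug/study regimen as in the dose modification column (Grade ≤1 or baseline, and after completion of any steroid taper); resume routine serum creatinine monitoring when creatinine returns to baseline.* The monitoring half then matches the Grade 1 row, which says "If creatinine returns to baseline, resume its regular monitoring per study protocol".

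The cost is one reworded bullet. Because the guidelines are the funder's text, the funder may need to agree. If the text cannot be changed, the same wording can go in as a study-specific note. Design, sample size, stopping boundaries and the renal monitoring schedule stay as they are.

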**For Grade 4:**

Permanently discontinue study drug/study regimen.

- If myasthenia gravis-like neurotoxicity present, consider starting AChE inhibitor therapy in addition to steroids. Such therapy, if successful, can also serve to reinforce the diagnosis.

***GUILLAIN-BARRE:***

- It is important to consider here that the use of steroids as the primary treatment of Guillain-Barre is not typically considered effective.
- Patients requiring treatment should be started with IV IG and followed by plasmapheresis if not responsive to IV IG.

| Myocarditis | Any Grade      | General Guidance  | For Any Grade:  |
|-------------|----------------|---|---|
|             |                | 
Discontinue drug permanently if biopsy-proven immune-mediated myocarditis.
   | 
 
– The prompt diagnosis of immune-mediated myocarditis is important, particularly in patients with baseline cardiopulmonary disease and reduced cardiac function.
 
– Consider, as necessary, discussing with the study physician.
 
– Monitor patients for signs and symptoms of myocarditis (new onset or worsening chest pain, arrhythmia, shortness of breath, peripheral edema). As some symptoms can overlap with lung toxicities, simultaneously evaluate for and rule out pulmonary toxicity as well as other causes (e.g., pulmonary embolism, congestive heart failure, malignant pericardial effusion). A Cardiology consultation should be obtained early, with prompt assessment of whether and when to complete a cardiac biopsy, including any other diagnostic procedures.
 
– Initial work-up should include clinical evaluation, BNP, cardiac enzymes, ECG, echocardiogram (ECHO), monitoring of oxygenation via pulse oximetry (resting and exertion), and additional laboratory work-up as indicated. Spiral CT or cardiac MRI can complement ECHO to assess wall motion abnormalities when needed.
 
– Patients should be thoroughly evaluated to rule out any alternative etiology (e.g., disease progression, other medications, or infections)
 
 |
|             | Grade 1 | 
No dose modifications required unless clinical suspicion is high, in which case hold study drug/study regimen dose during diagnostic
 | 
For Grade 1 (no definitive findings):
 
 
- Monitor and closely follow up in 2 to 4 days for clinical symptoms, BNP, cardiac enzymes, ECG, ECHO, pulse oximetry
 
   |

|  |   |   |
|--|---|---|
| 
(asymptomatic with laboratory (e.g., BNP) or cardiac imaging abnormalities)
   | 
work-up for other etiologies. If study drug/study regimen is held, resume after complete resolution to Grade 0.
  | 
(resting and exertion), and laboratory work-up as clinically indicated.
 
 
- Consider using steroids if clinical suspicion is high.
 
   |
| 
Grade 2, 3 or 4
 
(Grade 2: Symptoms with mild to moderate activity or exertion)
 
(Grade 3: Severe with symptoms at rest or with minimal activity or exertion; intervention indicated)
 
(Grade 4: Life-threatening consequences; urgent intervention indicated (e.g., continuous IV therapy or mechanical hemodynamic support))
 | 
 
- If Grade 2 -- Hold study drug/study regimen dose until resolution to Grade 0. If toxicity rapidly improves to Grade 0, then the decision to reinitiate study drug/study regimen will be based upon treating physician's clinical judgment and after completion of steroid taper. If toxicity does not rapidly improve, permanently discontinue study drug/study regimen.
 
If Grade 3-4, permanently discontinue study drug/study regimen.
 
 | 
For Grade 2-4:
 
 
- Monitor symptoms daily, hospitalize.
 
- Promptly start IV methylprednisolone 2 to 4 mg/kg/day or equivalent after Cardiology consultation has determined whether and when to complete diagnostic procedures including a cardiac biopsy.
 
- Supportive care (e.g., oxygen).
 
- If no improvement within 3 to 5 days despite IV methylprednisolone at 2 to 4 mg/kg/day, promptly start immunosuppressive therapy such as TNF inhibitors (e.g., infliximab at 5 mg/kg every 2 weeks). Caution: It is important to rule out sepsis and refer to infliximab label for general guidance before using infliximab.
 
- Once the patient is improving, gradually taper steroids over <math>\geq 28</math> days and consider prophylactic antibiotics, antifungals, or anti-PJP treatment (refer to current NCCN guidelines for treatment of cancer-related infections [Category 2B recommendation]).a
 
 |
| 
Myositis/Polymyositis
("Poly/myositis")
  | 
Any Grade
   | 
General Guidance
 
For Any Grade:
 
 
- Monitor patients for signs and symptoms of poly/myositis. Typically, muscle weakness/pain occurs in proximal muscles including upper arms, thighs, shoulders, hips, neck and back, but rarely affects the extremities including hands and fingers; also difficulty breathing and/or trouble swallowing can occur and progress rapidly. Increased general feelings of tiredness and fatigue may occur, and there can be new-onset falling, difficulty getting up from a fall, and trouble climbing stairs, standing up from a seated position, and/or reaching up.
 
- If poly/myositis is suspected, a Neurology consultation should be obtained early, with prompt guidance on diagnostic procedures. Myocarditis may co-occur with poly/myositis; refer to guidance under Myocarditis. Given breathing complications, refer to guidance under Pneumonitis/ILD.
 
                                 |

|  |  |   |
|--|--|---|
|  |  | 
Given possibility of an existent (but previously unknown) autoimmune disorder, consider Rheumatology consultation.
 
 
– Consider, as necessary, discussing with the study physician.
 
– Initial work-up should include clinical evaluation, creatine kinase, aldolase, LDH, BUN/creatinine, erythrocyte sedimentation rate or C-reactive protein level, urine myoglobin, and additional laboratory work-up as indicated, including a number of possible rheumatological/antibody tests (i.e., consider whether a rheumatologist consultation is indicated and could guide need for rheumatoid factor, antinuclear antibody, anti-smooth muscle, antisynthetase [such as anti-Jo-1], and/or signal-recognition particle antibodies). Confirmatory testing may include electromyography, nerve conduction studies, MRI of the muscles, and/or a muscle biopsy. Consider Barium swallow for evaluation of dysphagia or dysphonia.
 
 
Patients should be thoroughly evaluated to rule out any alternative etiology (e.g., disease progression, other medications, or infections).
 |
| Grade 1
(mild pain)  |  | 
 
- No dose modifications.
 
  |
| Grade 2
(moderate pain associated with weakness; pain limiting instrumental activities of daily living [ADLs]) |  | 
Hold study drug/study regimen dose until resolution to Grade <math>\leq 1</math>.
 
 
- Permanently discontinue study drug/study regimen if it does not resolve to Grade <math>\leq 1</math> within 30 days or if there are signs of respiratory insufficiency.
 
  |

